QEEG and Neurofeedback Training for the Treatment of Substance Use Disorders: A Randomized Controlled Trial

Addiction Unit, Sørlandet Hospital HF

17.03.2017

Approved by the Regional Committee for Medical and Health Research Ethics
on 04.05.2017 (No. 2017/746)

1. Relevance relative to the call for proposals

Substance use disorders (SUD) is considered one of the major public health concerns of our time, with high degree of comorbidity and far-reaching individual and societal implications. The dark figures are high, as only a small percentage of those affected seek help in treatment facilities, but it is assumed that between 10 and 20% of the population will experience problems related to excessive drug use in the course of their lives [1]. This makes SUD one of our most prevalent psychiatric conditions, compromising physical and psychological health and resulting in impairment in cognition, social relationships and quality of life (QoL), at high cost for society.

Of those who do seek treatment, relapse trajectories are discouraging. Some sources suggest that twelve-month relapse rates following cessation attempts from various classes of substance use can be more than 80% [2], implying that for the majority of those who enter traditional psychosocial or medication-based models of treatment relapses to drug use is common. In other words: the treatment of the disorder is as exceedingly complicated as is the disorder itself. A patient with a SUD typically requires comprehensive and life-long care across the different levels of service providers, from primary care to the specialist health care services, and case management for these individuals can be resource-intensive and complex. A systemic view of recovery is warranted, an interdisciplinary and integrative approach which aims to improve the physiological, psychological and social aspects of the disorder. New approaches to treatment, either new, stand-alone modalities or in conjunction with other therapies, are therefore constantly being sought.

2. Aspects relating to the research project

Background and status of knowledge

Traditionally, the dominant focus in addiction treatment has been on psychosocial approaches such as cognitive behavioral treatment, motivational interviewing, contingency management, 12-step programs, and pharmacological programs [3]. However, a growing awareness of the role of neurobiology in the development and maintenance of SUD [3, 4], has led to increasingly more international research interest being invested in efforts to develop and incorporate neuropsychological intervention methods into existing treatment paradigms [4, 5].

Through the use of modern brain imaging techniques such as quantitative electroencephalography methods (QEEG), in conjunction with low-resolution electromagnetic tomography (LORETA) or functional magnetic resonance imaging (fMRI), researchers have revealed that acute and chronic drug abuse can result in significant alteration of a person's brain activity [4, 6]. For instance, electroencephalography (EEG) investigations of patients with alcoholism have documented that even after prolonged periods of abstinence, they seem to have lower levels of alpha and theta waves and an excess of fast beta brain waves [7], making it difficult for them to relax. Following alcohol intake, however, the levels of alpha and theta brainwaves increase to normal levels. Such findings have led researchers to postulate that these individuals inadvertently use alcohol as a way of down-regulating their brainwave patterns to achieve the desired relaxed mental state. Conversely, psychostimulants can be used to "up-regulate" patterns which are associated with negative emotional states, such as depression. Thus, for the SUD patient, drug use can be a way of artificially normalizing these dysfunctional brain wave patterns.

Modern theories of cortical plasticity foster promise that such disturbed information processing can be reversible [8, 9]. One way of influencing brain activity directly is through EEG biofeedback. Also known as neurofeedback (NF), the method was first popularized for the treatment of alcohol dependence by the works of Eugene Peniston [10-12], and has been employed in the treatment of SUD for more than three decades. NF is a method aimed at reorganizing and normalizing brain wave patterns. Through electrodes placed on the scalp, oscillatory activity from the cortex is recorded and played back to the individual in the form of visual, auditory, and/or tactile stimuli, enabling shaping of the brain activity towards more functional patterns [13]. The aim of the NF training is to enable the

individual to develop skills for self-regulation of cortical activity. Because negative emotional states can trigger the urge to use drugs to achieve this regulation [2], neurofeedback can potentially prevent relapses through its calming effect on the central nervous system.

Peniston's encouraging outcome results in the eighties generated substantial interest in the addiction field, and efforts were made to replicate these findings. Several other studies using the Peniston protocol and its modifications reported cases with positive clinical effects, however, studies utilized primarily naturalistic design, sample sizes were small, description of methods insufficient and only few of these studies were published in mainstream peer-reviewed journals [14]. Consequently, the spread of the method has been slow, and it has not been applied systematically in addiction treatment. A recent review concluded that "Based on published clinical studies and employing efficacy criteria adapted by the Association for Applied Psychophysiology and Biofeedback and the International Society for Neurofeedback and Research, alpha theta training – either alone for alcoholism or in combination with beta training for stimulant and mixed substance abuse and combined with residential treatment programs, is probably efficacious" [14]. Since then, compiling empirical evidence, using alpha rhythms as well as other EEG band ranges, has demonstrated its efficacy for various forms of substance use disorders [15]. However, despite this growing evidence of its applicability, the method remains largely obscure and under-used in clinical applications for this patient population in Norway. To our knowledge, the addiction unit at the Clinic for Psychiatry and Addiction Medicine at Sørlandet Hospital is at present the only clinic nationwide applying the method systematically.

When neurofeedback was introduced and implemented as an adjunct treatment in our out-patient addiction clinic in 2011, many patients reported positive effects on a variety of comorbid symptomatology, and the retention rate for those who received the treatment was also significantly higher than the norm for this patient group. These observations were confirmed in a pilot study conducted at the clinic in 2012, in which the treatment was also rated positively by the patients [16]. Furthermore, data from subsequently admitted patients, measured by the same tools as in the pilot, have shown generally the same trajectory. These findings have spurred a motivation to conduct a larger, randomized controlled study to further investigate the role of NF in the treatment of SUD, this time with focus on its add-on effects to the treatment as usual (TAU) regime. Recognizing the high cost of treatment failure for society as large, as well as the high emotional cost for the individual, we wish to investigate whether the physiological effects of the treatment will help elicit positive emotional states which can strengthen coping behavior and aid patients in their efforts to become and remain abstinent. Thus, we believe that NF can play an important role in a relapse prevention paradigm and that its contribution can be captured with global patient-reported outcome measures such as well-being and QoL.

The current research proposal departs from previous studies in four important areas:

1. One of the challenges with a technology-driven intervention method such as NF is that research often lags behind the rapid technological development. Whereas most of the studies to date have utilized NF treatment protocols based on measuring subsets of the EEG activity, divided into band rangebandrange frequencies in the 4-30 Hz specter (such as Theta, Alpha, Beta rhythms), current clinical interest in some milieus has shifted to slow cortical potentials (SCP). SCPs are slow, event-related, direct-current shifts in the EEG, originating from the large cell assemblies in the upper cortical layer in the midline of the brain [17]. Newer software and hardware technologies have made it possible to isolate and process even slower bandwidths, so-called infra-low frequency training (ILF), i.e. frequencies below 0.1 Hz. This particular form of NF training seems to have the potential to influence the brain's resting state networks, which is thought to have a central role in underpinning overall brain function [18]. ILF training can thus be said to target core regulatory function of the central nervous system, rather than remediating specific deficits or diagnoses. This can explain the claimed wide applicability of the method across diagnoses and symptom categories. However, although favorably received in some clinical communities, the empirical support for the claims for ILF training is as of yet virtually non-existent. It is therefore important to fill this

apparent gap in the literature.

2. This study is among the few in the addiction treatment field that has QoL as its main outcome measure. The rationale behind this choice of outcome is that improvement of QoL can be viewed as an overarching aim of addiction treatment, a generic expression of the patient's global functioning and well-being. A high QoL has been found to correlate with positive affect, and can thus help maintain the motivation to stay sober. Nevertheless, in previous studies QoL is rarely assessed; reduction in substance use has been given main focus. If living without substance use is to be the goal for the SUD patient, this aim will simply not be perceived as "worth" striving towards if it is not associated with improved well-being in at least some facets of life. Consequently, patients may lose motivation and interest in their rehabilitative process [19].

3. Accordingly, the theoretical framework for this study will be to use NF as a strategy and potential tool in relapse prevention. Negative emotional states, such as anger, anxiety, depression, frustration, and restlessness are associated with higher rate of relapse to drug use [20]. By closely monitoring these variables throughout the project, we will be able to assess whether NF has a potential add-on effect on the patient's ability to cope with such negative emotions and the ensuing drug urge and cravings.

4. The proposed design has a stronger user involvement than previous research efforts in the field. User representatives with personal experience with NF will take an active part in the intervention and have regular dialogue meetings with participants, allowing informal exchanges about the method (e.g., possible effects and side-effects). We expect this element of the study to potentially boost the effect of the intervention. This way of boosting effects of other interventions has recently become a recommended strategy in the addiction treatment field [21].

Approaches, hypotheses, and choice of method

The overall aim of the study is to acquire more knowledge about the effectiveness of NF in the treatment of substance use disorders in general, specifically in relation to its effect on physical and psychological distress (e.g. sleep disturbances, anxiety symptoms etc.), and subsequently on its ability to improve QoL and prevent relapse. An RCT study will be undertaken to examine whether neurofeedback (NF) + treatment as usual (TAU) compared to TAU only can increase the QoL of patients with a SUD in the short and long term. We hypothesized that, compared to the TAU condition the NF + TAU condition would result in higher QoL at the end of treatment as well as at a 3- and 12-month follow-up. Included in our QoL assessment measure is perceived functioning in important areas such as work and social relations.

Our secondary outcome hypothesis is that the NF+TAU condition will result in better substance use outcomes as well as improvement in sleep quality, psychological distress, and symptoms of anxiety and depression at the end of treatment and at follow-up compared to controls. Drop-out rates will also be compared for the two groups, controlling for baseline demographic and severity variables.

In addition to the RCT, the project group will write up on an extended naturalistic cohort study initiated after the previous pilot, and investigate this cohort in relation to similar aims as described above.

Inclusion criteria

Patients with a substance use disorder referred to outpatient addiction treatment, aged >18 of both genders.

Exclusion criteria

Severe psychiatric disorders (e.g. psychosis) that have not been stabilized with e.g., medication (assessed as a part of the clinical process at the clinic). Severe cognitive impairment or language problems (inability to converse for interviews).

Experimental design

The proposed experimental study will have a two-group pre-post design with an intervention group (NF+TAU) and a control group (TAU). Participants will include patients referred to outpatient addiction treatment at two clinics within Sørlandet Hospital HF, in Kristiansand and in Arendal. Because regular attendance is desirable for participation in the project, certain clinical selection criteria will apply, but this will be handled not by the project group itself, rather it will reflect ordinary practice within the present clinical setting. Thus, patients are thought to be clinically eligible to the NF condition after having achieved an initial level of stable attendance at the clinic. This is congruent with the study's focus on relapse prevention.

Patients meeting the criteria for inclusion will be informed about the project and given the opportunity to participate. After providing written, informed consent, those patients who choose to participate will be randomly assigned to either NF training + TAU, or TAU alone. The allocation will be determined through notes prepared in sealed envelopes by an external researcher based on a block randomization design. As a part of the NF+TAU condition, participants will be invited to an informal dialogue session within a month of starting the intervention, in which a user representative will be available to answer potential questions and share individual experience concerning the treatment. The TAU participants will receive standard psychotherapeutic treatment, chosen according to individual needs and therapist preference.

The intervention will consist of 20 sessions of symptom-based NF tailored to the individual patient. Training will be conducted using the Othmer method of NF from EEGinfo, comprising bipolar, infra-low frequency training, with the inclusion of synchrony and alfa-/theta training as needed.

All participants will complete the inventory described below at the outset. The instruments are chosen for their ability to measure internal states associated with a risk of triggering urges and cravings leading to drug use. Cognitive function is assessed because impairment in this domain is associated with poorer treatment outcomes, including decreased treatment retention in SUD patients [22]. QEEG data will be recorded prior to and after the 5 months intervention period. These data will be analyzed by our cooperating partner at Norwegian University of Science and Technology (NTNU) to identify possible biomarkers for addiction, and to study the neurophysiological effects of neurofeedback.

Instruments

In addition to basic demographics and the Mini International Neuropsychiatric Interview (M.I.N.I.) to confirm the SUD diagnosis [23], the inventory includes the items and scales below:

Primary outcome

- Quality of life, measured with
 - QoL-10, a 10-item questionnaire which rates the patient's subjective experience of life quality. The respondents are asked to rate their physical and psychological health as well as the quality of their relationships on five-point Likert scales. The scale also includes a subscale about perceived functioning in areas such as work, sexual and social relations [24].

Secondary outcomes

- Perceived functioning/well-being:
 - Outcome Rating Scale (ORS), a visual analogue scale consisting of four subscales measuring the patient's perceived functioning in the personal, interpersonal and social domains, in addition to a general measure of his or her perceived QoL. The respondents are asked to rate their perceived functioning in these areas from very low to very high on a 10 cm, unmarked horizontal line [25]. This scale was included to corroborate on the measurement of perceived functioning in

the QoL-10 functioning subscale and to be used in the repeated measuring of perceived functioning to assess trajectories of change (see below).

- Negative affect:
 - Mental distress will be measured with the Symptom Check List-10 (SCL-10). This scale is a 10-item index with a four-point response scale that maps anxiety and depression. It is an abbreviated version based on the more comprehensive SCL-90, and has been shown to be valid indicators of psychological distress. The corresponding cut-off point to the conventional 1.0 for SCL-90 is 1.85 [26, 27].
 - Restlessness and trepidation, measured with a visual analogue scale (VAS) on which the respondents are asked to rate their level of uneasiness from “none” to “very high” on a 10 cm, unmarked horizontal line [28, 29].
- Substance use:
 - Measured by selected questions from the European version of the Addiction Severity Index (EuropASI), a multi-dimensional interview used to measure a variety of aspects related to substance use [30].
 - Measured with two visual analogue scales (VAS), one for alcohol consumption and one for drug use, on which the respondents are asked to rate their intake in the last week by inserting a mark on a 10 cm, unmarked horizontal line [28, 29].
 - Perceived severity of substance use: As the study includes persons with both alcohol and drug dependence, we will also include a short, overall substance use severity measure at baseline; the Survey of Readiness for AA Participation (SYRAAP) severity subscale [31].
- Physiological variables:
 - Sleep quality, measured with a visual analogue scale (VAS) on which the respondents are asked to rate their sleep quality from “worst perceivable” to “best perceivable” on a 10 cm, unmarked horizontal line [28, 29].
- Cognitive function:
 - Measured with the Montreal Cognitive Assessment (MoCA), a brief screening instrument sensitive to mild cognitive impairment. The scale samples behavior across 14 performance tasks that engage multiple cognitive domains including attention, language, visuospatial, executive, and memory. Total possible score is 30 points, and a score of 26 or greater is classified as within normal range, that is, without evidence of cognitive impairment [22].
 - Measured with the QIK test – a continuous performance test devised to yield a reliable pre-post measure on attentional variables. It is a go/no-go challenge test, known as a choice reaction time test. It measures speed, accuracy and consistency and compares data to norms.
- To assess the *trajectories of change* in the NF-TAU condition, a simple computer-based screening test will be administered weekly to each participant during the project period, measuring: a) alcohol and drug use, b) sleep quality, c) restlessness and trepidation and d) perceived functioning (ORS). These VAS scales have been described above.

The participants will be reassessed after treatment and at a 3- and 12- month follow-up period. Research assistants (RAs) blinded to the patient’s condition assignment will conduct the follow-up interviews. Efforts will also be made to examine non-completers. Respondents will be reimbursed NOK 250 (\$30) for completing the follow-up interviews.

Sample size calculation

Sample size calculation is based on a previous study of a similar population where patients had a mean QoL score at 0.57 (SD 0.17) [32]. A minimal clinical relevant improvement and between group difference is considered to be 0.10 [33]. A sample size of 40 in each group has an 80% power to detect a 0.10 mean difference between groups with a significance level (alpha) of 0.05 (two-tailed). The power calculation was carried out with StatMate ver. 2.0 (GraphPad Software, Inc., San Diego, CA, US). We expect a 20% attrition rate at follow-up, thus, 50 patients will be needed in each group.

Statistics

Baseline variables will be reported with descriptive statistics. Difference between randomized groups on primary outcomes will be assessed with Student's t-test. Secondary outcome will be assessed with appropriate tests, e.g., the weekly repeated measures will be analyzed with generalized estimating equation (GEE) to test for differences between groups.

3. The project plan, project management, organization and cooperation

Project group:

- Principle investigator and PhD supervisor: [name] PhD, Addiction Unit (ARA), Sørlandet Hospital HF (SSHF)
- Assistant supervisor: [name] MD/PhD: ARA, SSHF and University of Oslo
- Statistical supervisor: [name] PhD: Oslo Centre of Biostatistics and Epidemiology, Oslo University Hospital
- User representative: [name]
- Clinical neurofeedback specialist, [name], ARA, SSHF

Advisory board:

The advisory board consists of national and international specialists on neurofeedback and QEEG [34, 35]. In addition, we cooperate with a community based researcher who is our link to the local municipality [36].

- [name], Clinical Director, London Scientific Neurotherapy

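### The stated 80% power at 40 per group is about 74% on the plan's own inputs; secondarily, the available text ties the single primary test to none of the three QoL visits

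*Combined protocol and SAP*

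**What the plan says.** All references are to the combined protocol and SAP.

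*Sample size calculation.* The SD comes from an earlier study in a similar population, in which "patients had a mean QoL score at 0.57 (SD 0.17". The minimal relevant between-group difference is 0.10. The power statement is "A sample size of 40 in each group has an 80% power to detect a 0.10 mean difference between groups", at two-tailed alpha 0.05. Enrolment follows from it: "We expect a 20% attrition rate at follow-up, thus, 50 patients will be needed in each group".

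*Statistics.* "Difference between randomized groups on primary outcomes will be assessed with" Student's t-test. The section does not say whether the test is on follow-up scores or on change from baseline.

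*Approaches, hypotheses, and choice of method.* The main hypothesis is that "the NF + TAU condition would result in higher QoL at the end of treatment as well as at a 3- and 12-month follow-up".

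*Instruments.* The primary outcome is "QoL-10, a 10-item questionnaire which rates the patient's subjective experience of life quality", with no visit attached. The schedule reads "The participants will be reassessed after treatment and at a 3- and 12- month follow-up period".

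*Experimental design.* "The proposed experimental study will have a two-group pre-post design".

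*Dissemination and communication of results.* The planned papers include a main RCT paper on quality of life and a separate one on whether effects persist to 12 months.

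**The concern.** The power sentence supplies every input needed to check it, and it does not check. The 40 per group then carries into the enrolment target, so the plan credits itself with 80% power at its own expected attrition when the figure is lower. A funder, ethics committee or later reader interpreting a null result would take the chance of missing the minimal relevant difference to be 20%. On the printed inputs it is about 26%.

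The visit question is separate and smaller. Three visits sit in the main quality-of-life hypothesis, but one test and one sample size are given. If the groups differ significantly at one or two visits only, the available text does not settle whether the main hypothesis succeeded. The 20% attrition is also not tied to a particular follow-up visit, so the power calculation does not show which visit it serves.

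**Working it through.** **Inputs (Sample size calculation; Statistics).** Difference δ = 0.10; SD σ = 0.17; alpha 0.05 two-sided; n = 40 evaluable per group, equal groups; Student's t-test. I take the test to be on follow-up scores, because the printed SD belongs to a score with mean 0.57.

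**1. Reproducing the stated 80%.**

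- Standardised difference: 0.10 / 0.17 = 0.588.
- Noncentrality: 0.588 × √(40/2) = 0.588 × 4.472 = 2.631.
- Normal approximation: Φ(2.631 − 1.960) = Φ(0.671) = 74.9%.
- Noncentral t with 78 degrees of freedom: 73.8%.

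The stated 80% is not reproduced. The obvious variants do not reach it either:

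- one-sided 0.05 at n = 40: 83.2% (t), 83.8% (normal);
- all 50 per group retained: 83.0% (t), 83.7% (normal).

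For 40 per group to give 80% by the t-test, the difference would have to be about 0.108 or the SD about 0.158. Neither value is in the document.

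**2. Number needed for 80%.**

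- Normal: n = 2 × (1.960 + 0.842)² / 0.588² ≈ 45.4, so 46 per group.
- Noncentral t: 46.3, so 47 per group.

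| Evaluable per group | Power (t-test) |
|---|---|
| 40 | 73.8% |
| 45 | 78.8% |
| 46 | 79.7% |
| 47 | 80.6% |
| 50 | 83.0% |

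**3. Attrition.** The inflation step is correct: 40 / (1 − 0.20) = 50. The error lies in the 40. With 50 randomised, 80% power requires losses of at most 50 − 47 = 3 per group, which is 3/50 = 6%. Keeping 80% at 20% attrition would take 47 / 0.80 = 58.75, so 59 per group.

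**4. If change from baseline is meant.** With SD 0.17 at both time points and baseline–follow-up correlation r, the SD of change is 0.17 × √(2(1 − r)). Power at 40 per group is then 66% / 74% / 80% / 83% for assumed r = 0.4 / 0.5 / 0.57 / 0.6. The document gives neither r nor an SD of change.

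**5. Split results across the three visits (illustrative).** Assume a true 0.10 effect at every visit, the same n at each, and equal correlation between visits. The correlation is not in the document. I simulated three test statistics, each with mean 0.588 × √(n/2) (2.631 at n = 40, 2.941 at n = 50), against the t critical value with 1,000,000 draws. The table gives the chance that exactly one or two of the three visits are significant.

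| Assumed correlation | 40 per group | 50 per group |
|---|---|---|
| 0 | 57.8% | 42.2% |
| 0.5 | 39.9% | 30.2% |
| 0.7 | 30.6% | 23.4% |
| 0.8 | 24.8% | 19.2% |
| 0.9 | 17.5% | 13.5% |

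By hand at correlation 0 and n = 40, power per visit is Φ(2.631 − 1.991) = 0.739, and 1 − 0.739³ − 0.261³ = 0.579, in line with the simulated 0.578.

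**The case against.** **On power.** The strongest reply is that the t-test may be meant for change scores: the design is described as pre-post and the sample size section speaks of improvement. A correlation near 0.57 would then bring 40 per group to 80%. This does not rescue the sentence. The correlation is nowhere stated, a lower one gives less than 74%, and the only SD printed is that of the score itself. What stands is that the 74% holds for a test on follow-up scores and must be labelled so.

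A reader might also infer that the trial is too small to run or that enrolment must rise. The document does not support that. Power is 83% with full retention and about 74% at the expected loss. The defect is the stated figure.

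**On visits.** The pre-post label and the separate 12-month paper favour end of treatment as the deciding visit, with later visits showing durability. Under that reading multiplicity harms neither alpha nor power. The reading is fair, but these are hints. The hypothesis gives all three visits the same standing, and the attrition allowance is stated for follow-up.

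Three stronger inferences should be resisted:

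- *That the false-positive rate is inflated.* Counting any unadjusted visit as success would give a two-sided error of roughly 8 to 14% for assumed correlations of 0.9 down to 0. The document proposes no such rule, and its hypothesis joins the visits instead of offering them as alternatives.
- *That a split result is likely.* It exceeds one half only at zero correlation with 40 per group, which is hard to defend for one questionnaire repeated in the same patients.
- *That the trial has no primary time point at all.* Part of the text was not available for review, and the trial registration listed in the project time frame, which might name a visit, cannot be seen here.

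**Conclusion.** The power statement is wrong as written. On its printed inputs, for a t-test on follow-up scores, 40 per group gives about 74%, a shortfall of some 5 to 6 percentage points. This depends on no assumption beyond the type of score tested, and it applies whichever visit is primary.

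The visit point holds in a limited form: the available text designates no primary visit and no rule across visits. Its consequence depends on a rule that is not stated. With one pre-named visit there is no multiplicity effect. The 13 to 40% range for a split result is an illustration for correlations of 0.5 to 0.9, an equal true effect at all visits, and 40 to 50 evaluable per group.

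Both should be corrected before data are seen. Neither stops the trial.

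**What to change.** **Power sentence.** Replace it with: about 74% power with 40 evaluable per group for a 0.10 difference (SD 0.17, two-sided 0.05); about 79% with 45 and 83% with 50. State the attrition expected at the visit that carries the test. Enrolment of 50 per group can stay; the sponsor should know that 80% at 20% attrition would take about 59. If change from baseline is intended, say so and give the SD of change. The cost is a less favourable stated power.

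**Primary visit.** Name one visit, of the sponsor's choice, and attach the two-sided 0.05 t-test and the sample size to it. Either test the other two in a fixed, pre-stated order at 0.05, each only if the one before succeeds, or report them as estimates with 95% confidence intervals.

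This takes a few sentences, with no extra patients and no loss of alpha at the named visit. The price is that a later visit in the sequence cannot be confirmatory once an earlier test fails. Naming end of treatment makes the long-term claim secondary, while naming 12 months may expose the main test to the full 20% loss.

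### Two recruiting clinics: stratification by clinic is not stated and the primary t-test has no clinic term, so a small amount of precision is given up

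*Combined protocol and SAP*

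**What the plan says.** The Experimental design section (protocol section 2) draws participants from "patients referred to outpatient addiction treatment at two clinics within Sørlandet Hospital HF, in Kristiansand and in Arendal". The only description of the allocation in that section is: "The allocation will be determined through notes prepared in sealed envelopes by an external researcher based on a block randomization design". It gives no stratification factor, no separate list for each clinic and no block size.

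The Statistics section states: "Difference between randomized groups on primary outcomes will be assessed with Student's t-test". It lists no covariates for this test. Methods for secondary outcomes are left open, with GEE given as an example for the weekly measures.

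Clinic does not appear as a factor in allocation or analysis anywhere in the text available. The one covariate-controlled comparison, that of drop-out rates (under Approaches, hypotheses, and choice of method), uses baseline demographic and severity variables and does not name clinic.

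Two statements make some difference between clinics plausible. On clinical selection for regular attendance, the protocol says that "this will be handled not by the project group itself, rather it will reflect ordinary practice within the present clinical setting". The control treatment is "standard psychotherapeutic treatment, chosen according to individual needs and therapist preference".

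**The concern.** When a trial recruits at more than one clinic, clinic is a grouping known before randomisation that may predict the outcome. Here local practice governs selection and therapists choose the content of usual care, so mean QoL could differ between Kristiansand and Arendal. Good practice is to balance the arms within clinic and to carry clinic into the analysis. The plan does not state the first and omits the second.

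What is at stake is precision in a small trial, with 40 analysed per arm. Variation between clinics that a single model term could remove is left in the error against which treatment is tested. The plan also leaves open which of two designs is being run, and the appropriate analysis should match the design.

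**Working it through.** **Inputs from the Sample size calculation section:** SD of QoL 0.17; target difference 0.10; two-sided alpha 0.05; 40 analysed and 50 enrolled per arm.

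**Assumed, because the documents give no figure:** share from one clinic p = 0.6; difference between clinics in mean QoL d = 0.05 to 0.10; 0.17 is the total SD, clinics combined.

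**The plan's own figure.** n per arm = 2 × (1.96 + 0.842)² × 0.17² / 0.10² = 45.4, so 46 (47 by the t-distribution), against the stated 40. At 40 per arm the power is 74.9% (normal approximation) or 73.8% (noncentral t), against the stated 80%. The attrition step is right: 40 / 0.8 = 50. The shortfall is a separate matter. It is shown here only because 74.9% is the correct starting point for what follows.

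**Share of variance due to clinic,** p(1 − p)d² / 0.17²:
- d = 0.05: 0.24 × 0.0025 / 0.0289 = 2.1%
- d = 0.10: 0.24 × 0.0100 / 0.0289 = 8.3%

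**Effect of adjustment on the standard error.** Residual SD = √(0.0289 − 0.24d²); SE = SD × √(2/40); power ≈ Φ(0.10/SE − 1.96).

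| | SD | SE | Reduction in SE | Power, normal | Power, noncentral t |
|---|---|---|---|---|---|
| No clinic term | 0.1700 | 0.0380 | – | 74.9% | 73.8% |
| Clinic term, d = 0.05 | 0.1682 | 0.0376 | 1.0% | 75.8% | 74.7% |
| Clinic term, d = 0.10 | 0.1628 | 0.0364 | 4.2% | 78.4% | 77.4% |

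The gain is 0.9 to 3.6 points. Over a wider range (d = 0.03 to 0.10, splits from 50/50 to 80/20) clinic explains 0.5% to 8.7% of the variance, and adjusted power is 75.1% to 78.6% by the normal approximation.

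**Validity under one common list.** The variance of the contrast is 0.0289 × 2/40 = 0.001445. The part due to chance clinic imbalance is 0.24d² × 2/40 = 0.00003 (d = 0.05) to 0.00012 (d = 0.10), which is the same 2.1% to 8.3%. Chance imbalance is therefore already inside the t-test's standard error. Simulation (50/50 split, 40 per arm, 40,000 runs per setting) agrees. Type I error of the t-test is 4.8% (d = 0.05) and 5.0% (d = 0.10). Adding clinic raises power from 73.6% to 74.0% and from 74.0% to 77.0%.

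**Validity under one list per clinic.** Clinic is balanced by design, but the t-test still uses the larger standard error. With the 60/40 split its actual level is about 2 × [1 − Φ(1.96 / (1 − reduction in SE))]:
- d = 0.05: 1.96 / 0.990 = 1.98, giving 4.8%
- d = 0.10: 1.96 / 0.958 = 2.05, giving 4.1%

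The simulation with a 50/50 split gives 4.7% and 4.0%. The test is slightly conservative in both cases.

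**The case against.** The case against acting is reasonable, and much of it stands.

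- **The protocol is silent; it does not rule out per-clinic lists.** A reader might infer that allocation is known to be unrelated to clinic. The text does not support that. If the envelopes were prepared per clinic, the arms are balanced on clinic and only the mild conservatism remains.
- **No clinic difference is documented.** A reader might assume that each clinic has its own therapists and a distinct case mix. The protocol names two clinics within one hospital trust and refers to therapist preference; it does not say that staff are separate. The top of the assumed range, 0.10, equals the trial's whole minimal relevant difference, which is large for a gap between two such clinics.
- **Chance imbalance is not a second harm.** It is tempting to say that imbalance shifts the estimate and, in addition, that clinic variance inflates its error. Under a common list these are the same quantity.
- **Tail figures exaggerate.** With 50 per arm and a 60/40 split, 1.96 × √(0.24 × 2/50) = 0.19, which would move the contrast by 0.010 to 0.019, or 10% to 19% of the target. That takes a 1-in-20 imbalance as well as the assumed clinic gap. The median imbalance is 0.6745 × 0.098 = 0.066, a shift of 0.003 to 0.007.
- **Secondary methods are left open,** so they do not exclude a clinic term.

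None of this removes the core point. The primary analysis is specified without clinic, and under either reading of the allocation a model with clinic does as well or better at almost no cost.

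**Conclusion.** The plan does not state stratification by clinic, and its primary t-test omits clinic. The consequence is some lost precision under a common list, or a slightly conservative test (about 4% to 5% actual level) under per-clinic lists.

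The size is modest: about 2% to 8% of the variance, 1% to 4% of the standard error, and from under 1 to about 4 points of power at 40 per arm. These figures rest on an assumed 60/40 split and an assumed clinic difference of 0.05 to 0.10. If the clinics hardly differ, the gain is close to nil.

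A reader might infer that the treatment estimate is biased or the t-test invalid. Neither follows: the estimate is unbiased in expectation and type I error does not exceed its nominal level in any meaningful way. Nor does the sample-size shortfall add weight to this point; it needs its own correction. The documents also give no basis here for criticising the block sizes, which are simply not stated.

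**What to change.** 1. State whether the envelopes come from one list or one per clinic. If enrolment permits, prepare separate block sequences for Kristiansand and Arendal.
2. Whatever the answer, replace the primary t-test with a linear model for QoL that has treatment and clinic as fixed effects, specified before outcome data are examined by arm. Use the same clinic term in the secondary models and in the GEE. This can be done even if enrolment has begun.

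Suggested wording: The difference between arms in QoL-10 will be estimated from a linear model with treatment and clinic (Kristiansand, Arendal) as fixed effects, reported with a 95% confidence interval.

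The cost is one degree of freedom in the model and possibly one incomplete block per clinic. No extra patients, visits or data items are needed.
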